8.6 Breastfeeding

Breastfeeding is exclusionary and not allowed during the study. If a participant begins breastfeeding during the study, they will be discontinued from study treatment. The participant will continue to be followed on study, off study treatment through the end of the study period with evaluations per [section 6.1](#), except they will not be required to fast and will not have the FDG-PET/CT imaging performed and PK samples drawn.

9.0 CRITERIA FOR DISCONTINUATION

9.1 Permanent and Premature Treatment Discontinuation

- Drug-related toxicity (see [sections 8.1](#) and [8.2](#)).
- Requirement for prohibited concomitant medications (see [section 5.4](#)).
- Confirmed virologic failure (see [section 6.2.3](#)).
- Pregnancy or breast-feeding.
- Request by participant to terminate treatment.
- Clinical reasons believed life threatening by the physician, even if not addressed in the [Toxicity section](#) of the protocol.

9.2 Premature Study Discontinuation

- Participant repeatedly noncompliant (missing eight consecutive doses or more) with study medications as prescribed.
- Failure to start study treatment.
- Request by the participant to withdraw.
- Request of the primary care provider if s/he thinks the study is no longer in the best interest of the participant.
- At the discretion of the IRB/Ethics Committee, ACTG, Food and Drug Administration (FDA), NIAID, Office for Human Research Protections (OHRP), other government agencies as part of their duties, investigator, or industry supporter.

10.0 STATISTICAL CONSIDERATIONS

10.1 General Design Issues

A5415 is a double-blind, randomized, placebo-controlled, phase II trial to evaluate 24 weeks of CVC on TBR in the carotid arteries and aorta among individuals living with chronic HIV on ART with viral suppression. CVC or placebo for CVC will be administered for 24 weeks to participants. The total sample size will be 93 participants (62 in the CVC arm and 31 in the placebo arm).

10.2 Outcome Measures

Primary and secondary outcomes listed below will be addressed in the study's primary Statistical Analysis Plan, which will define the content of the primary statistical analysis report. This report will form the basis for the primary study manuscript(s) and results reporting to <https://ClinicalTrials.gov>. Outcomes of interest for secondary and exploratory objectives intended for subsequent publications are listed as other outcome measures.

10.2.1 Primary Outcome Measures

Change in arterial most diseased segment (MDS) 18-FDG-PET target-to-background ratio (TBR), measured in the carotid arteries and aorta, from baseline to week 24.

The standardized uptake value (SUV) of FDG will be measured in the carotid arteries, aortic root, and the left main coronary artery. The SUV is the decay-corrected tissue concentration of FDG (in kBq/mL) divided by the injected dose per body weight (kBq/g). TBR will be calculated for each vascular segment as the segment SUV divided by mean venous blood SUV.

NOTE: The MDS has been preferred as the primary outcome measure at the time of the study design. However, since this choice of endpoint is guided by studies in populations with chronic atherosclerotic disease that typically excluded individuals with active inflammatory diseases or HIV, the study team intends to re-evaluate this choice of primary outcome measure closer to the time of the analysis (prior to review of the arterial inflammation data) based on contemporary data at that time.

10.2.2 Secondary Outcome Measures

10.2.2.1 Change in aortic TBR (and other TBRs) from baseline to week 24

10.2.2.2 Change in SUV measured in the carotid arteries and aorta from baseline to week 24

10.2.2.3 Change in fasting glucose from baseline to week 24

10.2.2.4 Change in HOMA-IR from baseline to week 24

10.2.2.5 Change in biomarkers from baseline to week 22/24

10.2.3 Other Outcome Measures

10.2.3.1 Change in FDG uptake in visceral fat and lymph nodes from baseline to week 24

10.2.3.2 Change in adipocytokines (such as adiponectin) from baseline to week 24

10.2.3.3 Change in plasma CCR5 and CCL2 levels from baseline to week 22/24

10.2.3.4 Changes in myeloid derived suppressor cell (MDSC) frequencies as well as monocyte subsets (as defined by expression of CD14 AND CD16, expression of homing receptors: CX3CR1, CCR5, CCR2, and activation as determined by HLA-DR density and CD69 expression) from baseline to week 22/24

10.2.3.5 Changes in CD4 and CD8 T cell expression of CX3CR1, CCR2, CCR5, and activation as determined by expression of CD38 and HLA-DR from baseline to week 22/24

10.2.3.6 Change in fasting insulin from baseline to week 24

10.2.3.7 Change in fibrinogen and other coagulation markers from baseline to week 24

10.2.3.8 Changes in visceral adipose tissue area and volume, subcutaneous adipose tissue area and volume, fat density, and liver to spleen attenuation ratio (as a noninvasive measure of hepatosteatosis) by noncontrast CT from baseline to week 24

10.3 Randomization and Stratification

At study entry, participants will be randomized at a 2:1 ratio (CVC arm: placebo arm), using permuted blocks stratified by statin use. Institutional balance will not be used at randomization.

While enrollment is ongoing, enrollment limits will be increased to replace participants who are randomized but do not start treatment.

10.4 Sample Size and Accrual

The target sample size is 75 participants (50 in the CVC arm and 25 in the placebo arm) with baseline and follow-up PET/CT. To allow for some loss to follow-up and participants unwilling or unable to complete 2 scans, we plan to enroll 93 participants (62 in the CVC arm and 31 in the placebo arm) in this trial.

The primary analysis will focus on between-treatment arm differences in the within-participant changes in arterial MDS TBR (the measure of arterial inflammation by PET/CT). Based on a superiority trial design with two-sided $\alpha=0.05$, assuming a standard deviation (SD) of $0.065 \log_{10}$ TBR for change in MDS TBR, a total of 75 participants providing complete, evaluable data sets will ensure 80% power to detect a between-groups difference of $0.046 \log_{10}$ MDS TBR (which is a 10% reduction from baseline).

The assumptions underlying the power calculation are as follows:

- 1) The target effect size for the change in MDS TBR on therapy of 10% is based on the observation of a statin intensification study [46].
- 2) The assumed SD for change in (\log_{10}) MDS TBR of 0.065 is derived from the placebo arm of ACTG A5314.
- 3) The use of a two-sided, two-sample T-test with type-I error rate of 5%.

The assumption that 93 enrolled participants will provide 75 participants with evaluable data is derived by 20% total data loss due to drop-out after randomization (including premature discontinuation of study treatment and change in background ART drug class).

If the variability in the change in MDS TBR is lower than assumed (smaller SD) or the total data loss is lower than assumed, the statistical power to detect the targeted effect size for our primary analysis will be higher (see Table 10.4-1).

Table 10.4-1: Sample Sizes and Power Corresponding to Various Total Data Loss and Assumed SD

Total sample size	Total data loss	Evaluable sample size	Power	Assumed SD for change in MDS TBR (in \log_{10})
93 (62 + 31)	20%	75 (50 + 25)	80%	0.065
108 (72 + 36)	20%	87 (58 + 29)	80%	0.071
93 (62 + 31)	20%	75 (50 + 25)	85%	0.061
93 (62 + 31)	17%	78 (52 + 26)	83%	0.065

For secondary outcome measures (excluding the secondary imaging measures), the sample size of N=93 will provide 90% power to detect a 0.052 SD difference. This

assumes a 15% total data loss (lower since there will be no loss due to image scheduling or quality related issues).

We expect to have slow accrual completed over a period of 2 years. Full details of the accrual plan will be outlined in the Study Progress, Data, and Safety Monitoring Plan (SPDSMP). Participants who do not start study treatment will be replaced unless enrollment has been completed.

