2.1 Study Design

A5415 is a double-blind, randomized, placebo-controlled, phase II trial to evaluate 24 weeks of Cenicriviroc mesylate (CVC) to reduce arterial inflammation among individuals living with chronic HIV on ART with viral suppression. CVC or placebo for CVC will be administered for 24 weeks to participants. The target sample size was 93 participants (62 in the CVC arm and 31 in the placebo arm). The study enrolled between May 2023 and January 2024 with a final sample size of 110 participants.

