2.4 Overview of Sample Size Considerations

The target sample size is 75 participants (50 in the CVC arm and 25 in the placebo arm) with baseline and follow-up PET/CT. To allow for some loss to follow-up and participants unwilling or unable to complete 2 scans, the study planned to enroll 93 participants (62 in the CVC arm and 31 in the placebo arm). Final enrollment was 110 participants.

The primary analysis will focus on between-treatment arm differences in the within-participant changes in arterial MDS TBR (the measure of arterial inflammation by PET/CT). Based on a superiority trial design with two-sided $\alpha=0.05$, assuming a standard deviation (SD) of 0.065 \log_{10} TBR for change in MDS TBR, a total of 75 participants providing complete, evaluable data sets will ensure 80% power to detect a between-groups difference of 0.046 \log_{10} MDS TBR (which is a 10% reduction from baseline).

The assumptions underlying the power calculation are as follows:

- 1) The target effect size for the change in MDS TBR on therapy of 10% is based on the observation of a statin intensification study.
- 2) The assumed SD for change in (\log_{10}) MDS TBR of 0.065 is derived from the placebo arm of ACTG A5314.

3) The use of a two-sided, two-sample T-test with type-I error rate of 5%.

The assumption that 93 enrolled participants will provide 75 participants with evaluable data is derived by 20% total data loss due to drop-out after randomization (including premature discontinuation of study treatment and change in background ART drug class).

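### Protocol 10.4 claims 90% power at 0.052 SD for the non-imaging secondary outcomes; power there is about 5.5%, and 90% power needs about 0.79 SD

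*Protocol*

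**What the plan says.** Protocol section 10.4 sizes the trial on the primary PET outcome and then adds a statement for the secondary outcomes that are not imaging measures: "the sample size of N=93 will provide 90% power to detect a 0.052 SD difference". It says that this "assumes a 15% total data loss", less than the 20% used for the primary outcome because scan scheduling and image quality play no part.

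The sentence names no test or significance level of its own. The surrounding text supplies them:

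- **Arms.** Section 10.4: "we plan to enroll 93 participants (62 in the CVC arm and 31 in the placebo arm) in this trial".
- **Allocation.** Section 10.3: "participants will be randomized at a 2:1 ratio (CVC arm: placebo arm), using permuted blocks stratified by statin use".
- **Test.** The primary calculation in section 10.4 lists as an assumption "The use of a two-sided, two-sample T-test with type-I error rate of 5" per cent. Section 10.6 sets two-sided 0.05 for every test.
- **Analysis.** Section 10.6.3 analyses the key secondary endpoints by the primary method.

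SAP section 2.4 repeats the primary calculation but neither repeats nor corrects the secondary statement. It does record that "Final enrollment was 110 participants".

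**The concern.** A difference of 0.052 SD is very small. A trial with fewer than 100 participants cannot detect it reliably with a between-arm comparison, so either the number or its unit is wrong.

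This is the only power statement in either document for fasting glucose, HOMA-IR and the biomarkers, the outcomes that serve secondary objectives 1.3.1 and 1.3.2. A reader who relies on it would take a non-significant result as ruling out almost any effect. If the true sensitivity is much lower, such a result leaves moderate effects open.

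**Working it through.** **Inputs**

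- Enrolled: 62 + 31 = 93 (Protocol 10.4).
- Loss: 15%, so 93 × 0.85 = 79.05, about 79 evaluable. At 2:1 this is 53 + 26.
- Test: two-sample t-test, two-sided 5% (Protocol 10.4 and 10.6).

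**Method.** For a standardized difference d, the noncentrality is δ = d / √(1/n₁ + 1/n₂) on n₁ + n₂ − 2 degrees of freedom. Power is the probability that a noncentral t variable with that δ falls outside ± the 97.5% point of the central t.

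**Step 1: does the method match the plan's own?** The primary effect is 0.046 log10 TBR, which is −log10(0.9) rounded. For the first row of Table 10.4-1, d = 0.046/0.065 = 0.708, √(1/50 + 1/25) = 0.245 and δ = 2.89.

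| Evaluable | SD | Stated power | Recomputed |
|---|---|---|---|
| 50 + 25 | 0.065 | 80% | 81.4% |
| 58 + 29 | 0.071 | 80% | 80.4% |
| 50 + 25 | 0.061 | 85% | 85.9% |
| 52 + 26 | 0.065 | 83% | 82.9% |

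All four rows agree to within 2 points.

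**Step 2: the secondary statement.** √(1/53 + 1/26) = 0.2394, so at d = 0.052, δ = 0.052/0.2394 = 0.217. The critical value on 77 degrees of freedom is 1.991. Power is 5.5%, against a stated 90%.

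**Step 3: what the design can detect.** By the normal approximation, the difference detectable with 90% power is (1.960 + 1.282) × 0.2394 = 0.776 SD. The noncentral t gives 0.786 SD. The ratio to the printed figure is 0.786/0.052 = 15.1.

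| Evaluable | Power at 0.052 SD | 0.3 SD | 0.4 SD | 0.5 SD | 0.6 SD | 80% power at | 90% power at |
|---|---|---|---|---|---|---|---|
| 53 + 26 (93, 15% loss) | 5.5% | 24% | 38% | 54% | 70% | 0.68 SD | 0.79 SD |
| 62 + 31 (93, no loss; or 110, 15% loss) | 5.6% | 27% | 44% | 61% | 77% | 0.62 SD | 0.72 SD |

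The 110 reading of the second row uses 110 × 0.85 = 93.5 and assumes a 2:1 split. With 53 + 26, power is 50% at 0.475 SD.

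**Step 4: the sample size the sentence would need.** Total N = (1.960 + 1.282)² × 4.5 / 0.052², where 4.5 = 1/(2/3) + 1/(1/3) for 2:1 allocation. This is about 17,490 evaluable, or about 20,570 enrolled after 15% loss.

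**Step 5: other readings of the sentence**

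- All 110 with no loss (73 + 37, assumed split): 5.8% power at 0.052 SD; 90% power at 0.66 SD.
- One-sided 5% test, 53 + 26: 7.6%.
- Paired within-arm test, 53 to 93 pairs: under 8%.
- Decimal slip for 0.52 SD, between arms: 57% with 53 + 26, 65% with 62 + 31.
- 0.052 as a log10 TBR difference at the primary SD: 0.052/0.065 = 0.80 SD, with 91.0% power at 53 + 26 and 89.7% at 50 + 25.

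Only the last comes near 90%. Working backwards, 0.786 × 0.065 = 0.0511 for 53 + 26 and 0.805 × 0.065 = 0.0523 for 50 + 25. The printed 0.052 therefore fits the 20% loss used for imaging slightly better than the 15% that the sentence states.

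**The case against.** The strongest reply is that this is a labelling slip in a supporting remark. If 0.052 was computed in log10 TBR units, the planners had about 0.80 SD in mind and their calculation was roughly sound; the factor of 15 then measures a wrong label and not a wrong belief. That origin is plausible, but the documents do not show how 0.052 was derived. It also does not save the text, because the sentence expresses the difference in SD units and excludes imaging outcomes, to which a TBR unit cannot apply.

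A second reply is that little depends on the sentence. The sample size was set by the primary outcome, accrual is closed, SAP 2.4 omits the statement, no test or analysis set uses it, and the secondary results will be reported with confidence intervals. All of this stands. It limits the consequence to interpretation and makes the correction cheap, but it does not make the figure right.

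A third is that SAP 2.0 replaced the t-test with a linear regression adjusted for statin use (sections 7.2.3 and 8), so the t-test figures are approximate. That is fair. However, bringing 0.786 SD down to 0.052 SD would need a residual SD of 0.052/0.786 = 6.6% of the unadjusted SD. Statin use would have to explain about 99.6% of the variance (1 − 0.066²), which is not credible.

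Finally, figures for the 110 enrolled rest on an arm split and a loss rate that the documents do not give for that cohort. This stands too, and those figures should carry the assumption openly.

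**Conclusion.** The statement is wrong as written. Under the plan's own assumptions (93 enrolled at 2:1, 15% loss, two-sided 5% two-sample t-test), power at 0.052 SD is about 5.5%. The difference detectable with 90% power is about 0.79 SD, and with 80% power about 0.68 SD. Effects below about 0.47 SD would be missed more often than found, whereas the text implies 90% detection of an effect about one ninth that size. The larger accrual helps only modestly: about 0.72 SD for 90% power if the 110 split 2:1 and lose 15%.

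The conclusion does not depend on the loss rate, sidedness or exact arm split, since every variant tried at 0.052 SD gives less than 8% power. The primary sample size reproduces and is unaffected, as are the analyses and trial conduct.

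**What to change.** Replace the sentence in Protocol 10.4, or, if the protocol will not be amended again, put the correction in SAP 2.4:

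> Under the two-sided 5% two-sample t-test used for planning, 93 participants with 15% data loss (53 + 26) give 90% power to detect a difference of about 0.79 SD (80% power: about 0.68 SD). For the 110 enrolled, assuming the same loss and a 2:1 split (about 62 + 31), the corresponding figures are about 0.72 SD and 0.62 SD.

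If the actual evaluable counts per arm are available when the text is revised, use them in place of the assumed 62 + 31. If 0.052 was meant in other units, state the unit, the SD and the outcome it refers to.

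The cost is one sentence and a less favourable stated sensitivity. Nothing changes in the primary sample size, the analyses or the conduct of the trial.

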10.5 Data and Safety Monitoring

The ACTG CTSG SMC will review study conduct and adverse events over time, broken by treatment arms. Efficacy review or treatment arm comparisons will not be included in the SMC interim reviews. There is no other formal stopping guideline for this study. See [section 7.4](#) for study monitoring timelines and other details.

10.6 Analyses

All statistical tests will be two-sided with a nominal alpha level of 0.05. No adjustment for multiple testing will be performed. Stratification will be taken into account in all analyses unless stated otherwise.

Since the goal of the study is to determine the biological activity of CVC on vascular inflammation, the primary analytic approach will be per protocol and limited to participants who remain on study treatment without change in background ART drug class per the study design.

Baseline is defined as pre-entry for TBR and SUV, average of entry and pre-entry for immunology markers, and entry for all other outcome measures.

10.6.1 Analysis Sets

Per-protocol population is defined as all participants who receive study treatment over 22 weeks and remain on the same ART drug class during the entire study period.

Safety analysis population is defined as all participants who initiated study treatment.

10.6.2 Primary Analyses

The primary analysis of efficacy will be limited to the per-protocol population.

TBR will be transformed for analyses on the \log_{10} scale and back transformed to percentage change for interpretation and presentation. Change in TBR will be summarized by mean and 95% confidence interval for percentage for each treatment arm and compared between the arms using a T-test, stratified by statin

use. A 95% confidence interval for the relative between-arm shift will also be estimated.

10.6.3 Secondary Analyses

A sensitivity analysis for the primary analysis will include participants in the per-protocol analysis described in the primary analysis above as well as participants with data available for evaluation completed at premature treatment or study discontinuation that is after week 12 as long as they are on treatment within 7 days of the evaluation.

Supplementary analyses for the primary analysis will exclude participants with confirmed HIV-1 RNA >200 copies/mL at any time during the course of the study and extensive periods of ART interruption (see SAP for more detail).

Key secondary endpoints ([section 10.2.2](#)) will be analyzed in the same manner (also per-protocol) as in the primary analysis.

For immunology markers, two blood draws will be performed at baseline (pre-entry and entry) and week 22/24 (week 22 and week 24) and the measurements will be the average of two values in order to reduce intra-participant variability. Outcome measurements may be transformed for analyses on the \log_{10} scale, as appropriate.

Safety will be evaluated by summarizing the nature and rate of AEs (signs and symptoms, laboratory values, SAEs) for the safety analysis population.

10.6.4 Handling of Missing Data and Sensitivity Analyses

Multiple imputation will be used to account for missing data due to unreadable or missed scans.

A sensitivity analysis for the primary analysis will include a complete case analysis.

10.7 Unblinding

Planned Unblinding

Participants will be unblinded at completion of the study. Please refer to ACTG SOP-123 Unblinding Participants for details.

Sudden/Unplanned Unblinding

- The decision to unblind one or more arms of an ongoing study is made by the team in conjunction with the relevant Scientific Committee and the Executive Committee. This can occur based on a recommendation from the SMC or the results of another trial (also see the DAIDS SOP “Termination of a Trial or a Single Treatment Arm”).

- If the decision is made to unblind, participants should be unblinded as soon as possible. Unblinding is conducted through the DMC, which sends treatment assignments to the sites soon after the unblinding decision. Every effort should be made by the sites to contact participants who have completed follow-up in order to explain the study results.
- When a treatment comparison is unblinded based on an interim analysis, the results of that interim analysis must be reported in publications. Data from visits that occurred before the interim review but that were not in the database at the data cutoff date have little potential for bias and may be reported with a comment. Data from visits that occurred after unblinding are potentially biased and must not be used if the intent is to claim that all the data are from a blinded study. In unblinding due to both “interim analysis” and the “other trial results” situations, if analyses are reported on clinical data or samples taken after the unblinding date, the conditions under which these data were gathered must be made clear in any publication.

11.0 PHARMACOLOGY PLAN

11.1 Pharmacology Objectives

11.1.1 To determine the impact of INSTI and NNRTI-based ART on CVC trough estimates.

11.1.2 To determine the impact of CVC treatment on the trough exposure of ART.

11.1.3 To determine the association between CVC trough exposure and the primary treatment outcome (i.e., reduced arterial inflammation).

11.2 Pharmacology Study Design

Participants will be enrolled who are stabilized on an NNRTI-based or unboosted INSTI-based ART regimen for ≥ 48 weeks prior to study entry. PK data available to date is specified in [section 2.1](#) (“Supporting Pharmacokinetic Data from Allergan/AbbVie”). Appropriate dosage adjustments will be made for participants on EFV-based ART based on these prior data. Data for those on INSTI-based ART is limited to DTG where modest reduction in CVC exposure (28% and 29% reduction in CVC Cmax and AUC 0-24 hr, respectively) was detected. Therefore, to provide information for CVC PK in individuals living with HIV on these regimens and to provide ART PK in the context of CVC specifically in individuals living with HIV, a sparse PK design will be completed. Since CVC should be taken with meals, information about whether or not dosing is done with food will be collected.

